**NCT02080637**

**Document Date: March 21, 2016**

**Title: Safety, Pharmacokinetics (PK) and Hemodynamic Effects of Ambrisentan in Single Ventricle Pediatric Patients.**

**1. Protocol Synopsis**

|   |  |
|---|--|
| Protocol Title                     | Safety, Pharmacokinetics (PK) and Hemodynamic Effects of Ambrisentan in Single Ventricle Pediatric Patients.  |
| Product                            | ambrisentan  |
| Objective:                         | To evaluate the safety, PK and hemodynamic effect of ambrisentan in pediatric patients with single ventricle heart defects.  |
| Study Design:                      | Randomized, double blind, placebo controlled PK, safety, and hemodynamic efficacy study.   |
| Study Population:                  | Up to 20 patients ages $\geq$ 24 months and $\leq$ 120 months with single ventricle cardiac lesions; Undergoing elective Fontan surgical palliation.   |
| Number of Subjects:                | Up to 20 subjects  |
| Duration of Subject Participation: | Until 1 month after administration of the last study drug administration   |
| Inclusion criteria                 | 
 
1. Age <math>\geq</math> 24 months; <math>\leq</math>120 months.
 
2. History of congenital heart disease with severe hypoplasia of a right or left ventricle.
 
3. Undergoing Fontan surgery as part of standard clinical care.
 
4. Availability and willingness of the parent/legally authorized representative to provide written informed consent and, as appropriate, assent from the child.
 
  |
| Exclusion criteria                 | 
 
1. History of serious adverse event related to ambrisentan administration.
 
2. History of ambrisentan exposure within 48 hours of the study.
 
3. Presence of pulmonary venous obstruction.
 
4. Treatment with cyclosporin
 
5. Any of the following – as determined by the attending physician 
 
a. Significant hemodynamic instability
 
b. Sepsis.
 
c. Need for ECMO support.
 
 
 
6. Renal failure defined as serum creatinine <math>></math> 2 times higher than the upper limit of normal.
 
7. Liver dysfunction defined as alanine aminotransferase or aspartate aminotransferase <math>></math> 3 times higher than the upper limit of normal.
 
8. Thrombocytopenia defined as a platelet count <math><</math> 50 000 cells/<math>\mu</math>L.
 
9. Leukopenia defined as white blood cells <math><</math> 2500 cells/<math>\mu</math>L.
 
10. Anemia defined as hemoglobin <math><</math> 8mg/dL
 
11. Atrial hypertension (mean LA pressure <math>></math> 12mm Hg)
 
 |
| Dose Schedule:                     | Once daily oral administration   |
| Estimated Start:                   | Jan 2014   |
| Estimated Finish:                  | Jan 2016   |
| Duration of therapy                | 3 days   |

|                                   |   |
|-----------------------------------|---|
| PK/PD:                     | Blood samples will be obtained at various time points after drug administration. PK parameters will be estimated by non-compartmental analysis using WinNonLin software. PD parameters will include change in hemodynamic endpoints (Fontan pressures, calculated cardiac index, pulmonary vascular resistance and brachial artery flow mediated vasodilation measured by ultrasound) |
| Statistical Consideration: | This protocol has sufficient enrollment to provide pilot safety and PK data and to allow assessment of the hemodynamic effects of ambrisentan on pulmonary vascular resistance and Fontan pressures.  |

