### **Exclusion Criteria**

1. History of serious adverse event related to ambrisentan administration.
2. History of ambrisentan exposure within 48 hours of the study.
3. Presence of pulmonary venous obstruction.
4. Treatment with cyclosporin
5. Any of the following – as determined by the attending physician
  - a. Significant hemodynamic instability
  - b. Sepsis.
6. Renal failure defined as serum creatinine  $>$  2 times higher than the upper limit of normal.

7. Atrial hypertension defined as a common mean atrial pressure  $> 12$  mm Hg via direct measurement (central line) or a Fontan mean pressure  $> 22$  mm Hg in a patient with no atrial line.

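### The synopsis and Section 6 give different exclusion lists and nothing says which governs: four laboratory exclusions appear only in the synopsis, and the hemoglobin limit among them does not work as printed.

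*Combined protocol and SAP*

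**What the plan says.** Section 1 (Protocol Synopsis) has eleven numbered exclusions. Five of them are laboratory limits:

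- creatinine above 2 times the upper limit of normal;
- "Liver dysfunction defined as alanine aminotransferase or aspartate aminotransferase" above 3 times the upper limit of normal;
- "Thrombocytopenia defined as a platelet count" below 50 000 cells/µL;
- "Leukopenia defined as white blood cells" below 2500 cells/µL;
- "Anemia defined as hemoglobin" below 8, with the unit printed as mg/dL.

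The synopsis also lists "Need for ECMO support" and a mean left atrial pressure above 12 mm Hg.

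Section 6 (Exclusion Criteria) has seven items, numbered without a gap. Its only laboratory item is "Renal failure defined as serum creatinine", with the same limit as the synopsis. It keeps "Significant hemodynamic instability" and sepsis but does not list ECMO. Its atrial hypertension item uses the same 12 mm Hg limit, measured "via direct measurement (central line) or a Fontan mean pressure" above 22 mm Hg where there is no atrial line. Section 12 (Risk/Benefit assessment) repeats that surrogate.

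Section 10 (Baseline/Pre-Dose Assessment) requires every eligibility criterion to be met, but does not say in which list. No section gives an order of precedence.

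**The concern.** Eligibility has to give one answer for each child. Here two staff members could reach opposite decisions on the same child, and each could cite the protocol. The usual convention that the body prevails over the synopsis does not settle the matter safely, because here the synopsis is the longer list: following Section 6 alone drops four laboratory exclusions.

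What is at stake is safety at entry and consistent eligibility decisions, in a study of up to 20 children dosed soon after Fontan surgery. Some of the missing items relate to matters that the protocol itself raises. Section 5 anticipates reduced hepatic elimination in these children, and Section 12 discusses falling hemoglobin on the drug. The hemoglobin item adds a separate problem, because the only entry threshold for it is printed in a unit that makes it inoperative.

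**Working it through.** No sample size, power or error rate is involved. The check sets the two lists side by side, with synopsis item 5 split into its three parts.

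| Element | Synopsis | Section 6 |
|---|---|---|
| Prior serious event on ambrisentan | yes | yes |
| Ambrisentan exposure within 48 hours | yes | yes |
| Pulmonary venous obstruction | yes | yes |
| Cyclosporin | yes | yes |
| Hemodynamic instability | yes | yes |
| Sepsis | yes | yes |
| ECMO | yes | absent |
| Creatinine > 2 × upper limit of normal | yes | yes |
| ALT or AST > 3 × upper limit of normal | yes | absent |
| Platelets < 50 000 cells/µL | yes | absent |
| White cells < 2500 cells/µL | yes | absent |
| Hemoglobin < 8 (printed mg/dL) | yes | absent |
| Atrial pressure > 12 mm Hg | yes | yes, plus Fontan mean > 22 mm Hg if no atrial line |

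**Counts.** The synopsis has 13 elements: 7 the same in Section 6, 1 with the same limit but a wider definition there, and 5 absent (7 + 1 + 5 = 13). Section 6 has 7 + 1 = 8 elements. Of the 5 laboratory limits, Section 6 keeps 1, so 5 − 1 = 4 are missing.

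**Conflicts.** Three numeric limits stand in both lists: 48 hours, creatinine at 2 times the upper limit of normal, and atrial pressure at 12 mm Hg. All three agree, so there are 0 numeric conflicts.

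**Unit.** 8 mg/dL ÷ 1000 = 0.008 g/dL. Read literally, no child falls below this.

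**Consequence by case**

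| Child | Synopsis alone | Section 6 alone | Both together |
|---|---|---|---|
| ALT/AST, platelets or white cells beyond the synopsis limit | excluded | eligible | excluded |
| Low hemoglobin | not excluded as printed | no limit | not excluded as printed |
| No atrial line, Fontan mean > 22 mm Hg | rule not named | excluded | excluded |

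The cases assume that the child meets every other criterion. Applying both lists together resolves the first and third rows but not the second.

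**The case against.** The best counter-argument is that exclusion criteria are cumulative. Section 10 asks for all of them to be met, and the limits printed in both lists agree, so a careful team would apply everything printed. This is a reasonable reading, and it would remove the split on liver tests, platelets and white cells. But it is a reading and not an instruction: Section 10 names neither list, and Section 6, which carries the selection criteria, looks complete. Cumulative reading also leaves the hemoglobin limit inoperative.

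It can also be said that the hemoglobin unit is an obvious slip that clinical staff would see through. That is likely. The same unit is used for hemoglobin in the Section 12 background text, which makes a fault of text extraction improbable; that second use is clerical and sets no entry limit. An entry threshold should still not depend on the reader correcting it.

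Other safeguards exist: the healthcare provider's approval before enrollment (Section 7), ICU monitoring at the first dose (Section 12) and discontinuation in the patient's interest (Section 14). They reduce the risk, but none sets an entry limit.

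Several stronger readings are tempting and are not supported:

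- **A child on ECMO could enter under Section 6.** That list still excludes significant hemodynamic instability, which largely covers the case.
- **The Fontan surrogate is a rival rule.** Section 12 presents it as a stand-in for raised left atrial pressure, so it elaborates the synopsis item and does not contradict it.
- **The inclusion lists define different populations.** One speaks of severe hypoplasia and the other of underdevelopment, but Section 5 uses the latter idea for these same lesions, and nothing shows that any child would be classified differently. Assent is named only in the synopsis, but it belongs to the consent process, and consent pages are not in this copy.
- **The laboratory limits cannot be applied because no time of assessment is given.** This is missing detail, not a contradiction. Section 10 describes a pre-operative panel from usual care, Section 10 (Hospitalization Procedures) prefers recorded values nearest to dosing, though not expressly for eligibility, and Section 12 refers to routine daily post-operative laboratory tests.

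**Conclusion.** The concern holds in a bounded form. Four laboratory exclusions stand in the synopsis and not in Section 6, with no statement of which list governs. For three of them (liver tests, platelets, white cells), eligibility depends on which list is read, unless both are applied. For the fourth, hemoglobin, Section 6 has no limit and the synopsis limit, at 0.008 g/dL as printed, excludes no one. The ECMO and Fontan surrogate differences are minor.

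This is an entry rule that is wrong as written and bears on safety, so it should be fixed. A reader might infer that the two lists set conflicting thresholds, or that the trial's results are compromised. The documents support neither: the three shared numeric limits agree, and no sample size, endpoint or planned analysis changes. Nor can a number of affected children be given, because the documents do not say how often such laboratory values occur in Fontan candidates. The conclusion rests on the printed text alone and takes no view on which criteria are clinically right.

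**What to change.** Reconcile the exclusion lists in Section 1 and Section 6, together with the atrial pressure text in Section 12 (Risk/Benefit assessment), into one list stated identically in the synopsis and Section 6. Correct the hemoglobin unit in the synopsis. Which criteria and thresholds apply is for the clinical team to decide.

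The cost is protocol wording only. The usual-care pre-operative panel in Section 10 already contains creatinine, ALT, AST, platelets, white cells and hemoglobin, so limits judged on that panel need no added test.

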## 2. Purpose of the Study

The purpose of the study is to evaluate the safety, pharmacokinetics (PK) and pharmacodynamics (PD) of ambrisentan in children with single ventricle heart defects that are undergoing Fontan (stage III) surgical palliation. This is a double blind, placebo controlled study. The primary objective of this Phase I/II study is to assess the plasma PK, safety and PD of oral ambrisentan in children with surgically palliated single ventricle heart defects. A secondary objective will be to assess whether ambrisentan improves post-operative outcomes including amount and duration of chest tube drainage and hospital length of stay.

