## 4. Design and Procedures

This is a single-center, randomized, blinded PK study of ambrisentan in children ages  $\geq 24$  months and  $\leq 120$  months with single ventricle anatomy. There will be up to 20 subjects enrolled; 16 will receive ambrisentan and 4 will receive placebo. A small placebo control group is warranted to ensure that any treatment effect is not a result of post-operative improvement. Patients will be enrolled at the time of their routinely scheduled Fontan surgery.

**Initial Dose:** Oral ambrisentan 2.5 – 5 mg, single dose, once daily (nasogastric and gastrostomy tube administration will be considered only when a nasogastric or gastrostomy tube is already in place as part of routine post-operative care). Subjects will be randomized by Investigational Drug Services (IDS) to placebo (n=4) or oral ambrisentan (n=16) using permuted blocks. Subjects will receive either an oral suspension (2.5 or 5mg) or a 5mg tablet depending on their ability to swallow a tablet. To begin to ensure safety, the initial 5 subjects enrolled in the study (at least 4 active drug) will receive a dose of 2.5mg in a liquid suspension prepared by IDS. After enrollment of these subjects we will perform a preliminary PK/safety analysis and evaluate ambrisentan exposure. If the drug is well tolerated (no grade III or greater adverse events) and exposure is less than the target exposure of 500-800ng/mL, then we may increase the dose to 5mg/dL provided via tablet in those able to take a tablet or suspension for all others. If drug exposure is less than 100ng/mL then we will enroll additional study subjects to ensure that at least 16 study subjects achieve adequate drug exposure. If drug exposure is in the target range then we will continue to enroll study subjects to receive the 2.5mg suspension.

As summarized below, study drug will be discontinued for any grade 3 or greater adverse event. If this occurs then IDS will be permitted to unblind the study patient to allow for appropriate adverse event reporting. Drug administration will start on post-operative day #1 with initiation of oral feeds. Study drug/placebo will be prepared and delivered to the patient bedside by investigational drug services and administered orally. Subjects will continue on study drug for 3 days.

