## 5. Study medication

### Rationale for Dose Selection

Preliminary data from 16 children with pulmonary hypertension using once-daily doses of 5 mg demonstrate similar  $C_{max}$  and  $AUC_{24hr}$  to those seen in adult patients. This PK study included children and adolescents ages 2 years – 18 years including 9 subjects age  $\leq 10$  years. Weight ranged from 13kg to 52 kg. The half-life of elimination was 7.6 hours (range 5.4–15.3 hours), and there was improvement in hemodynamic parameters (mean pulmonary arterial pressure  $55\pm 18$  mm Hg decreased to  $45\pm 20$  mm Hg after initiation of ambrisentan,  $p=0.04$ ). Ambrisentan was well tolerated in all patients with no serious adverse events. In post-operative Fontan patients, I anticipate decreased bioavailability due to post-operative bowel wall edema but also decreased hepatic elimination. I will perform a preliminary PK/PD analysis after enrolling the first 5 subjects (at least 4 active drug) and adjust the dosing to achieve target peak concentrations of 500–800 ng/mL, a range that has demonstrated therapeutic efficacy as well as safety in adults. To maintain blinding, we will request that ambrisentan levels be sent from the commercial

laboratory directly to IDS. IDS will remove study patient identifiers and then forward the drug levels for PK analysis and determination of dose adjustment.

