## **13. Data Analysis & Statistical Considerations:**

There will be up to 50 subjects enrolled and receiving drug in this study. Additional subjects will be enrolled to ensure that at least 20 subjects have at least 4 evaluable PK samples and that at least 16 subjects have ambrisentan peak exposure > 100ng/dL. Subjects who have only 1 evaluable sample will be included in the analysis. Descriptive statistics such as number of observations, mean, median, 95% confidence interval, standard deviation, standard error, minimum, and maximum will be presented for continuous variables (such as age, weight, etc.). Other descriptive statistics such as counts, proportions, and/or percentages will be presented to summarize discrete variables (such as race, sex, etc.). Pharmacokinetic parameters will be calculated using non-compartmental analysis using WinNonlin software (Pharsight Corporation, Mountain View, CA). As previously mentioned, there will be an interim PK analysis that may alter the dosage.

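### Four placebo children cannot ensure that a hemodynamic effect is not post-operative recovery, and no between-arm estimate is planned; state the real precision and report the difference with its 95% CI

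*Combined protocol and SAP*

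**What the plan says.** The synopsis (Section 1, Statistical Consideration) states that enrollment is sufficient for pilot safety and PK data and "to allow assessment of the hemodynamic effects of ambrisentan on pulmonary vascular resistance and Fontan pressures". Section 4 sets the allocation, "16 will receive ambrisentan and 4 will receive placebo", and gives the reason for the control arm: "A small placebo control group is warranted to ensure that any treatment effect is not a result of post-operative improvement". Section 2 makes pharmacodynamics part of the primary objective and adds a secondary objective to "assess whether ambrisentan improves post-operative outcomes including amount and duration of chest tube drainage and hospital length of stay".

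No section gives an effect size, SD, alpha, power or target precision for a hemodynamic or post-operative endpoint. Section 14 describes hemodynamics by univariable statistics, as observed values and changes from baseline. Section 13 lists a 95% confidence interval among the descriptive statistics for continuous variables, but not for a difference between arms.

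The number of subjects is inconsistent. The synopsis and Section 4 say up to 20, and Section 4 also allows additional subjects if exposure is low. Section 7 speaks of consenting up to 50 to reach up to 20 evaluable. Section 13 says: "There will be up to 50 subjects enrolled and receiving drug in this study".

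**The concern.** Children recover over the first days after a Fontan operation, so a before/after fall in pressure on drug mixes drug effect with recovery. The placebo arm is the only part of the design that can separate the two. It has four children, and no planned analysis sets their change against that of the treated children.

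Two misreadings then become easy. A fall on drug could be reported as placebo-controlled because a placebo group existed. A difference whose interval includes zero could be reported as an adequate assessment that found no effect. The second risk applies equally to chest tube drainage and length of stay, for which Section 2 asks whether the drug improves outcome.

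**Working it through.** **Plan's own figure.** There is none to reproduce: the 20 subjects come with no derivation. The check is therefore what precision the stated numbers give.

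**Inputs.** 16 ambrisentan and 4 placebo (Section 4). 50 subjects at most (Section 13), read at the same 4:1 ratio as 40 and 10. Assumed, because the plan gives neither: two-sided 5%, and a common SD of change in both arms. Results are in units of that SD, so they need no outside effect size.

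**Step 1. Interval for the difference in change.** Half-width = t(0.975; n1+n2−2) × √(1/n1 + 1/n2).

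- 16 v 4: 2.101 × √(1/16 + 1/4) = 2.101 × 0.559 = **1.17 SD**.
- 40 v 10: 2.011 × √(1/40 + 1/10) = 2.011 × 0.354 = **0.71 SD**.

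**Step 2. Recovery trend from placebo alone.** Half-width = t(0.975; n−1)/√n. For n = 4: 3.182/2 = **1.59 SD**, using the SD of those four children. If the SD is pooled over both arms (18 df), it is 2.101/2 = 1.05 SD. Either way, the four children leave a recovery change of about 1 SD or more in either direction open.

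**Step 3. Detectable difference.** Exact two-sample t-test (non-central t, 18 df), 80% power: **1.66 SD** at 16 v 4. A true difference of a full 1.0 SD has about 39% power.

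**Step 4. Is there an analysis behind the placebo arm?**

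| Section | What it asks or plans |
|---|---|
| 4 | Placebo arm separates drug effect from recovery |
| 1 | Enrollment sufficient to assess hemodynamic effects |
| 2 | Whether the drug improves post-operative outcomes |
| 14 | Univariable summaries of hemodynamics and change from baseline |
| 13 | Descriptive statistics; no difference between arms |

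The first three rows need a comparison between arms. The last two do not contain one.

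**Step 5. Direction of the remaining uncertainty.** Section 10 takes pressures from central lines that are in place for routine care. Children whose lines are out contribute no pressure, so the widths above are the best case for 16 and 4. The documents give no rate from which to quantify the loss.

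**The case against.** The strongest reply is that this is a small Phase I/II study, that it calls its safety and PK data pilot data, that it claims no power, and that it plans no test whose failure could be misread. Much of this stands. No stated calculation is wrong, and a pilot may be small. But in the synopsis sentence the word pilot qualifies safety and PK; the hemodynamic clause carries no such limit. The Section 4 claim concerns what the control group can do, and interval width answers that whether or not a test is planned.

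A stronger reading is tempting, and the documents do not support it. A reader might take the fall cited under Rationale for Dose Selection ("mean pulmonary arterial pressure $55\pm 18$ mm Hg decreased to $45\pm 20$ mm Hg after initiation of ambrisentan", p=0.04) as the design effect and conclude that the trial has 16% power, with an interval of about ±21 mm Hg. Three things stand against this.

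- The figure is dose rationale: "Preliminary data from 16 children with pulmonary hypertension", uncontrolled, and on mean pulmonary arterial pressure. The plan never uses it as a target difference.
- The 16% assumes that all 16 children gave paired pressures. Sixteen is the PK sample; no number is given for the pressure comparison. With the same p=0.04, power at 16 v 4 would be 21% for 12 pairs, 28% for 9, 33% for 8 and 48% for 6.
- The mm Hg scale does not carry over. Section 6 excludes children without an atrial line whose mean Fontan pressure exceeds 22 mm Hg, and the SD of change in Fontan pressure is not given.

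Nor does it follow that the study can neither establish nor exclude a benefit: an observed difference above about 1.17 SD would exclude zero.

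**Conclusion.** The concern holds in SD units. At 16 v 4 the arm difference is estimated to about ±1.2 SD, the placebo mean to about ±1.6 SD, and 80% power needs about 1.7 SD. Four placebo children can therefore separate only a very large drug effect from recovery, and they do not ensure anything. Reading Section 13 as 40 v 10 narrows the interval to about ±0.7 SD but does not rescue the wording. The absence of a planned between-arm estimate is independent of these figures.

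The numbers rest on a two-sided 5% level, a common SD, and complete data in all 20 children. The fault lies in unsupported statements of what the design can do and in a missing estimate. It is not an arithmetic error, and it does not argue against running a small study.

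**What to change.** 1. In Section 14, add the ambrisentan-minus-placebo difference in change from baseline, with its 95% CI, for each hemodynamic endpoint. Do the same for the post-operative outcomes in Section 2 (difference between arms with 95% CI), and word that objective as estimating a difference.
2. Replace the sufficiency claim in the synopsis and the control-group sentence in Section 4 with: *With 16 ambrisentan and 4 placebo children, differences in hemodynamic change will be estimated to about ±1.2 SD; only very large differences could be distinguished from post-operative recovery, and an interval that includes zero will not be read as absence of effect.*
3. Reconcile 20 and 50 subjects across Sections 1, 4, 7 and 13, and restate the precision for the number chosen.
4. If a safety bound is added, state its basis: zero events in 16 gives a one-sided 95% upper bound of 1 − 0.05^(1/16) = 17% (two-sided 95%: 1 − 0.025^(1/16) = 21%).

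The cost is protocol wording and one added estimate per endpoint from data already collected. No extra patients or procedures are needed; the stated claim becomes more modest.
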